13.2 Definition of Dose-Limiting Toxicity (DLT)/Moderate Toxicity

With Amendment v09: A two level toxicity attribution scale will be used. In terms of attribution, all recorded adverse events will be classified as either related or unrelated to the study drug. Prior to this amendment a five level attribution scale (definite, possible, probable, unlikely, unrelated) was used.

A DLT will be defined as any of the following toxicities that occur during cycle 1, per CTCAE version 4.03, and are considered related to the study drug:

(Note: All adverse events will be considered relevant to determining dose-limiting toxicities and reporting unless the event can clearly be determined to be unrelated to the drug.)

Hematologic toxicities:

- For participants with less than 5% bone marrow blasts by morphology, with the exception of Grade 4 neutropenia, Grade 3 or 4 hematologic toxicity that does not resolve to Grade 2 by Day 49 (21 days after the day 28 cycle).
- For participants with less than 5% bone marrow blasts by morphology, Grade 4 neutropenia (absolute neutrophil count $<0.5 \times 10^9/L$) persisting up to Day 42 after the start of treatment.

Non-Hematologic toxicities:

- Any grade ≥ 3 non-hematologic toxicity for ≥ 7 days, with the exception of nausea not controlled by medical management within 72 hours.
- Any treatment related toxicity that prevents the administration of 80% of 8-chloro-adenosine during the first cycle of therapy.
- Delay in start of cycle 2 by more than 14 days due to drug-related non-hematologic toxicity.

Moderate toxicity will be defined as any grade 2 non-hematologic toxicity and occurs during cycle 1, per CTCAE v4.03, with the exception of:

- Allergic rhinitis
- Fatigue
- Sweating
- Weight gain or loss
- Alopecia
- Dry skin
- Nail or pigmentation changes
- Pruritus
- Hot flashes
- Flatulence
- Mouth dryness
- Nausea and vomiting without the use of maximal anti-emetic treatment
- Sense of smell or taste disturbance
- Erectile impotence
- Irregular menses
- Libido
- Oligospermia
- Tumor lysis syndrome
- Electrolyte/metabolic toxicity unable to be corrected within 48 hours
- Other grade 2 toxicity may be excluded pending PI and Data Safety Monitoring Committee (DSMC) review and approval

(Note: All adverse events will be considered relevant to determining moderate toxicities and reporting unless the event can clearly be determined to be unrelated to the drug.)

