5.2 Treatment cycle definition

Participants will be treated in 28-day treatment cycles until disease relapse, progression, unacceptable toxicity, withdrawal of consent, or other protocol specified parameters to stop treatment.

Once a treatment cycle has began (i.e. the Day 1 dose administered) if there is a hold in administering the study agent (see section 6.3.2), **missed doses may be made up if the criteria to resume treatment are met within 48 hours, or by Day 5 of the treatment cycle, whichever is later**. Otherwise missed administrations will not be made up, and treatment will resume with the next cycle (assuming start of cycle criteria are met). Should a hold or delay in treatment occur, after the last dose is administered in a given cycle, there will be a 21 day break, which may result in a delay in the start of the subsequent cycle.

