6.3.2 Dose Modifications and Treatment Interruptions

The table below details the specific dose modifications and treatment interruptions for administration of 8-chloro-adenosine; they are to be used in agreement with the information in Section 6.3.1. Unless listed in Table 6.3.2, treatment will continue without interruption or dose modification. Start of cycle criteria will apply to initiate a new cycle of therapy (Section 6.2).

Table 6.3.2 Dose Modifications and Interruptions to 8-Chloro-adenosine Administration*

Adverse Event	Treatment Modification
Non-Hematologic toxicities considered RELATED to 8-chloro-adenosine in all participants:	
Grade 3 toxicity except for the following: 
 • vomiting, nausea, diarrhea that responds to maximum medical therapy • electrolyte imbalance, fatigue, anorexia, asthenia, stomatitis, mucositis, infection, dermatitis 	Hold study treatment until resolution to \leq Grade 2. Resume at pre-hold dose.
Grade 4 toxicity:	Hold study treatment until resolution to \leq Grade 2. Resume at 1 dose level reduction unless the toxicity is a grade 4 electrolyte imbalance correctable within 48 hours or grade 4 vomiting that responds to maximum medical therapy within 48 hours. In such cases patients can resume treatment at the assigned dose without reduction at the Physician's discretion.
Hematologic toxicity RELATED to 8-chloro Adenosine	
Grade \geq 3 peripheral blood cytopenia not resolving to \leq Grade 2 by day 49 from start of cycle in patients who have less than 5% bone marrow blasts	No additional cycles of study drug will be administered
Other unspecified Non-Hematologic Toxicities considered UNRELATED to study agent	
Other unspecified events of any grade considered unlikely or not related to study agent.	Maintain treatment with study agent. Interruption of study treatment is permitted if the investigator consults with the Principal Investigator to determine that this is in the best interest of the participant.

*: See section 5.2 for additional criteria to resume, make up missed doses.

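### Section 13.2: the Grade 2 electrolyte exception is reversed, and the DLT nausea exception, read literally, exempts uncontrolled severe nausea

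*Combined protocol and SAP*

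**What the plan says.** Section 13.2 defines two kinds of cycle 1 event.

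- **DLT.** One bullet covers related non-hematologic toxicity of Grade 3 or higher lasting at least 7 days, "with the exception of nausea not controlled by medical management within 72 hours". Two further bullets cover "Any treatment related toxicity that prevents the administration of 80% of 8-chloro-adenosine during the first cycle of therapy" and "Delay in start of cycle 2 by more than 14 days due to drug-related non-hematologic toxicity".
- **Moderate toxicity.** This is any Grade 2 non-hematologic event outside a list of exceptions. The list includes "Electrolyte/metabolic toxicity unable to be corrected within 48 hours", and also nausea and vomiting that occurred without maximal anti-emetic treatment. It ends with an open item: "Other grade 2 toxicity may be excluded pending PI and Data Safety Monitoring Committee (DSMC) review and approval".

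Under Section 13.3, two patients with moderate toxicity or one with a DLT end dose-doubling, and dosing then depends on DLTs alone. The MTD is the highest level with at most 1/6 DLTs (Sections 13.3 and 13.4). Section 13.6 reuses the DLT definition for the phase II accrual halt at an unacceptable toxicity rate of 33% or more.

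Table 6.3.2 (Section 6.3.2) governs holds and reductions. Its Grade 3 row spares "vomiting, nausea, diarrhea that responds to maximum medical therapy". Its Grade 4 row spares "grade 4 electrolyte imbalance correctable within 48 hours" from dose reduction.

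**The concern.** An exception list normally removes events that are minor or quickly managed. The electrolyte item removes those that are not: as written, persistent Grade 2 disturbance is ignored and transient disturbance counts. The nausea clause, on its plain grammar, does the same at DLT level.

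The two items bear on different decisions. The electrolyte item helps to decide how fast the dose rises from 400 mg/m². The nausea clause feeds the 3+3 counts, the MTD and the phase II halt. Both event types are foreseeable. Section 6.1.2 lists hypercalcemia, hyperglycemia and hypouricemia in the earlier CLL patients (regardless of attribution), and lists nausea for other adenosine analogues.

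**Working it through.** The plan states no figure on this point, so the check compares passages and counts doses.

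**1. Electrolyte item**

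| Place | Treated leniently when the imbalance |
|---|---|
| Section 13.2, Grade 2 exception | cannot be corrected within 48 hours |
| Table 6.3.2, Grade 4 row | can be corrected within 48 hours |

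The two run in opposite directions. The Grade 3 row of Table 6.3.2 spares electrolyte imbalance without any condition, so it is no comparator. The open item at the end of the list permits further exclusions, so corrected events could be removed case by case. Nothing brings an uncorrectable Grade 2 event back in.

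Reach: the starting dose is now 400 mg/m², so one doubling is left. If doubling continues, 800 mg/m² is next. If two moderate toxicities end it, 400 mg/m² is expanded and the next level up is 600 mg/m². The item does not enter the DLT count. Electrolyte toxicity of Grade 3 or higher lasting 7 days or more is still a DLT.

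**2. Nausea clause**

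Two readings are possible. Literally, uncontrolled nausea is exempt. Alternatively, nausea is an exception to the 7-day duration and becomes a DLT at 72 hours (3 days). Three points favour the second:

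- Nausea that stays at Grade 3 or higher for 7 days is already uncontrolled at 72 hours, so the literal reading leaves the 72-hour limit with no work to do.
- The moderate list exempts Grade 2 nausea only where maximal anti-emetics were not used. Refractory Grade 2 nausea therefore counts, and it would be odd to ignore a worse form.
- Table 6.3.2 spares only nausea that responds to treatment.

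**3. Which patients the literal wording would misclassify**

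Inputs: five daily doses per cycle (Section 5.5); a hold for related Grade 3 or higher nausea that does not respond to treatment (Table 6.3.2); and Section 5.2, under which "missed doses may be made up if the criteria to resume treatment are met within 48 hours" or by Day 5, whichever is later. Assume dosing on schedule, Grade 3 nausea beginning after dose k on Day k, and the hold beginning when the next dose is due on Day k+1.

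- Share of cycle 1 drug given = k/5.
- Earliest end of a 7-day event = Day k+7.
- Last make-up day = the later of Day 5 and Day (k+1)+2 = Day k+3.

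| k | Share given | Earliest end | Last make-up day | Caught by the 80% bullet? |
|---|---|---|---|---|
| 1 | 1/5 = 20% | Day 8 | Day 5 | Yes |
| 2 | 2/5 = 40% | Day 9 | Day 5 | Yes |
| 3 | 3/5 = 60% | Day 10 | Day 6 | Yes |
| 4 | 4/5 = 80% | Day 11 | Day 7 | No, 80% was given |
| 5 | 5/5 = 100% | – | – | No |

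For k = 4 or 5, a cycle 2 delay of more than 14 days is still a DLT. The exception names nausea only, so accompanying vomiting or anorexia of Grade 3 or higher for at least 7 days also counts. What remains is isolated refractory nausea after dose 4 or 5, with cycle 2 delayed by 14 days or less.

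**4. Effect of one such patient**

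In phase I, 0/3 becomes 1/3 (doubling ends if still under way, and three more patients are treated), or 1/6 becomes 2/6 (escalation stops and the level is not the MTD). In phase II, one more event enters the rate that triggers the halt for DSMC review.

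**The case against.** The strongest reply is that no competent investigator would apply the nausea clause literally. The Grade 2 nausea item and Table 6.3.2 point clearly to the 72-hour threshold, the other DLT bullets catch early onset, and few patients would have isolated week-long nausea after dose 4 or 5. This largely stands and limits the consequence. It does not repair a DLT definition whose grammar says the reverse of its likely intent.

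On electrolytes, the item affects a single dose step. Amendment v09 follows the amendment that set the 400 mg/m² start, so that step may already be past. Correcting the item could also speed escalation, because corrected events would no longer count. Section 6.1.1 reports no toxicity attributed to the drug in humans. All of this is fair, and the net direction of the present error is unknown.

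Discretion exists elsewhere: the RP2D may be set below the MTD, and safety is reviewed quarterly. Those reviews do not correct the counts themselves.

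A reader might infer that the plan deliberately disregards severe uncontrolled nausea, or that the MTD will be set too high as a result. The documents support neither. Their other provisions on nausea point the opposite way, most such events would be caught by another bullet, and no event rate is given from which a bias could be estimated. A reader might also take the phase II effect as stopping the trial. Section 13.6 halts accrual for DSMC review.

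**Conclusion.** Both exceptions are wrong as written and should be corrected. The electrolyte item is reversed, with no sensible alternative reading. Its reach is the choice between 600 and 800 mg/m² after 400 mg/m², not the DLT count or the MTD. The nausea clause is defective in wording rather than in evident intent. It alters a classification only in the residual case set out above, where it would change a 3+3 count or the phase II toxicity rate by one event.

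The size is unknown, probably small and possibly zero. The conclusion assumes that holds follow Table 6.3.2 and that doses are given on schedule. The nausea window cannot be put firmly in days: Table 10.0, footnote c, allows 7 extra days for the start of cycles 2 to 4, so it is unclear from which day the 14-day delay is counted.

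**What to change.** - **Electrolyte item.** Exempt Grade 2 electrolyte or metabolic toxicity that is *corrected* within 48 hours. Cost: one line of amendment text. Corrected events would no longer end doubling, so some courses could go from 400 straight to 800 mg/m² where the present text would lead to 600.
- **Nausea clause.** Remove it from the 7-day bullet and add a separate bullet making nausea of Grade 3 or higher a DLT when medical management has not controlled it by 72 hours. If the sponsor means the 7-day rule to apply to nausea as well, simply delete the exception. Cost: the 72-hour rule is stricter than 7 days, may add DLTs, and can bring in three more patients at a level. Deleting the exception would add no more DLTs than that.
- **Recorded data.** If the MTD has not been declared, check cycle 1 events already recorded against the corrected wording. This is one pass through existing data, with no new collection.

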13.3 Dose Escalation/Expansion

The phase I study will follow a modified 3+3 design. During dose-doubling, enrollment and dose escalation of a cohort will be on the basis of the occurrence of moderate and/or dose limiting toxicities (DLTs). If dose-doubling is ended by a single DLT in cycle 1 or two occurrences of 'moderate' treatment-related

toxicity, subsequent dosing will be based on DLT only. DLT and moderate toxicity incidence will be based on toxicity events encountered during the first cycle of 8-chloro-adenosine treatment.

This modified design involves an initial accelerated dose escalation stage (dose-doubling over 'a' levels) that may be ended by a single dose-limiting toxicity (DLT) in cycle 1 or two occurrences of 'moderate' treatment-related toxicity as defined in section 13.2. During the initial accelerated stage of accrual, cohorts of up to 3 patients will be enrolled and the dose level will be escalated by increments of 100% (skipping 'b' dose levels). If two patients encounter moderate toxicity or one patient encounters DLT during cycle 1, the current dose level will be expanded and the accelerated stage will end; dose-doubling will stop. At the conclusion of the accelerated stage, dose escalation will occur over 'a' and 'b' dose levels according to the following rules*:

- If zero out of 3 evaluable patients has a DLT in cycle 1 then the next dose of 8-chloro-adenosine will be tested.
- If 1 out of 3 evaluable patients has a DLT in cycle 1, three additional patients will be assessed at the same dose of 8-chloro-adenosine.
- If 2 out of 3 patients have a DLT in cycle 1, dose escalation will cease and the next lower dose level will be expanded. Note: If 2 of 3 experience DLT on dose level -1, the trial will be stopped. Dose levels below 50mg/m² will not be considered.
- If 1 out of 6 evaluable patients has a DLT in cycle 1, then dose escalation to the next dose of 8-chloro-adenosine will continue.
- If 2 or more out of 6 patients have a DLT in cycle 1, dose escalation will cease and the next lower dose level will be expanded. Note: If 2 of 6 experience DLT on dose level -1, the trial will be stopped. Dose levels below 50mg/m² will not be considered.

The highest dose level that produces $\leq 1/6$ DLTs in cycle 1 will be the maximum tolerated dose (MTD). Patients may continue therapy unless there is unacceptable toxicity, disease relapse/progression or withdrawal of consent.

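### Section 13.2 counts a grade 2 event toward ending the 400-to-800 mg/m² doubling but can ignore a brief related grade 3-4 event; its electrolyte exception also runs the wrong way

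*Combined protocol and SAP*

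**What the plan says.** Section 13.2 gives three routes by which a related non-hematologic event in cycle 1 is a DLT. The first is grade 3 or higher lasting 7 days or more, with a nausea exception. The second is "Any treatment related toxicity that prevents the administration of 80% of 8-chloro-adenosine during the first cycle of therapy". The third is "Delay in start of cycle 2 by more than 14 days due to drug-related non-hematologic toxicity".

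The lesser category reads: "Moderate toxicity will be defined as any grade 2 non-hematologic toxicity and occurs during cycle 1". A list of exceptions follows. One is "Electrolyte/metabolic toxicity unable to be corrected within 48 hours". The last lets the PI and DSMC exclude further grade 2 events.

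Section 13.3 uses both counts during dose-doubling: "If two patients encounter moderate toxicity or one patient encounters DLT during cycle 1, the current dose level will be expanded", and the accelerated stage then ends. After that, "subsequent dosing will be based on DLT only".

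Since amendment v07 the starting dose is 400 mg/m² (level 3a). The next doubled level is 800 mg/m² (4a), and the intermediate level is 600 mg/m² (3b).

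**The concern.** Moderate toxicity is meant as an early warning. It ends the doubling before a DLT has occurred, and the synopsis counts it even in patients who are replaced. Such a signal should not weaken as events become more severe. Here it can: an event graded 2 is counted, and the same event graded 3 or 4 may drop out of both counts if it is brief.

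At stake is whether the next cohort goes from 400 straight to 800 mg/m², or whether 400 is expanded and 600 comes next. The earlier CLL experience (Section 6.1.2) shows that severe events of the relevant types occur: hypercalcemia reached grade 4, and hyperglycemia, abdominal pain and back pain reached grade 3. These are listed regardless of attribution, Section 6.1.1 says that none was attributed to the drug, and no durations or patient counts are given. They show that the types are plausible and supply no rate.

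**Working it through.** The plan states no figure on this point, so the check applies the definitions to cases.

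**1. Which brief grade 3-4 events escape both definitions?** Each case below is related, non-hematologic and under 7 days, with no cycle 2 delay beyond 14 days.

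- *Starts after Day 5.* Dosing is complete, so the 80% route cannot apply.
- *Held doses are made up.* Section 5.2: "missed doses may be made up if the criteria to resume treatment are met within 48 hours", or by Day 5 if that is later. At full dose nothing is lost.
- *Grade 3 with no hold required.* Table 6.3.2 exempts "electrolyte imbalance, fatigue, anorexia, asthenia, stomatitis, mucositis, infection, dermatitis", and also nausea, vomiting and diarrhea that respond to treatment.
- *Grade 3 costing one dose.* Dosing resumes at the pre-hold dose: 4 × 400 = 1600 of 5 × 400 = 2000 mg/m², which is 80%. The 80% has been given, so the route is not met.
- *Grade 4 costing one dose.* Table 6.3.2 generally resumes one level lower. Table 5.3.1 makes that 300 mg/m².

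| Dose lost after grade 4 | Drug given (mg/m²) | Share of 2000 |
|---|---|---|
| 2 | 400 + 3 × 300 = 1300 | 65% |
| 3 | 2 × 400 + 2 × 300 = 1400 | 70% |
| 4 | 3 × 400 + 300 = 1500 | 75% |
| 5 | 4 × 400 = 1600 | 80% |

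If 80% is read by amount of drug, losing dose 2, 3 or 4 is a DLT and only the loss of dose 5 escapes. If it is read by number of doses, every row is 4/5 = 80% and escapes. Table 6.3.2 also allows correctable grade 4 electrolyte imbalance and controlled grade 4 vomiting to resume without reduction; those follow the grade 3 arithmetic.

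**2. Does other text close the gap?** Section 13.3 refers back to 13.2. The notes that all adverse events are relevant unless clearly unrelated concern attribution and do not change the grade limits. The discretionary clause removes grade 2 events and adds nothing.

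**3. Apply the doubling rule to three patients at 400 mg/m².**

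| Cohort | DLT | Moderate | Next step |
|---|---|---|---|
| 3 of 3 with only escaping grade 3-4 events | 0 | 0 | 800 mg/m² opens |
| 2 of 3 with one countable grade 2 event each | 0 | 2 | 400 expanded, doubling ends, 600 next |

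Sections 13.1 and 13.3 also speak of two occurrences instead of two patients. The first row is unchanged, because nothing is counted.

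**4. Direction of the electrolyte exception.** Section 13.2 exempts the event that cannot be corrected within 48 hours, so the one that can be corrected counts. Table 6.3.2 is lenient in the opposite direction: grade 4 imbalance correctable within 48 hours may resume without reduction. That 13.2 is a drafting reversal is an inference, but the comparison supports it well.

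**The case against.** - *Grade 4 events are partly covered.* A reader might infer that any brief grade 4 event costing one dose goes uncounted. By amount of drug that is not so for doses 2 to 4, as the first table shows. The gap is wider for grade 3 than for grade 4.
- *The deciding body sees the events.* Section 7.2 puts doses and resulting adverse events into the PMT report, and the PMT decides escalation. DSMC review, the holds and reductions of Table 6.3.2, and an RP2D that may be set below the MTD also remain. It would be wrong to infer that brief severe events are hidden or that the affected patient is unprotected. What is missing is a rule that makes these events stop the doubling.
- *A site may count a resolving event as it passes through grade 2.* The text does not direct this. The reading also misses an event that skips grade 2 or resolves through an excepted type such as fatigue. If every such event is counted this way, the effect is nil.
- *The accelerated stage may already have ended when the start moved to 400 mg/m².* The documents do not say. If it had, moderate toxicity no longer matters. The current Sections 13.1 and 13.3 still prescribe doubling.
- *Tolerating brief, manageable grade 3 events is a legitimate choice.* This stands, and the fix should respect it. It does not explain why grade 2 events should count for more than grade 3-4 events.

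**Conclusion.** The concern holds for the literal text, with high confidence: the definitions are not monotone in severity, and the 48-hour electrolyte exception is reversed relative to Table 6.3.2. It should be fixed.

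Its size is one decision, 400 to 800 mg/m² against 400 expanded with 600 next, because later dosing uses DLTs alone. A reader might want a probability that the doubling wrongly continues. The documents do not support one: they give no related event rates, no durations and no share of severe events that would go uncounted, and the CLL list cannot supply them. The conclusion assumes that the accelerated stage is still open and that sites do not already count resolving events at grade 2.

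**What to change.** 1. Define moderate toxicity as related non-hematologic toxicity of grade 2 or higher in cycle 1 that does not meet the DLT definition, each event counted once at its highest grade. This also settles the resolving-event question.
2. Change the electrolyte/metabolic exception to toxicity that is corrected within 48 hours, and let it apply at any grade. Limiting it to grade 2 would count a grade 3 imbalance corrected within hours, against Table 6.3.2, which requires no hold for it.
3. Apply the other listed exceptions to grade 2 only, and extend the existing PI/DSMC exclusion route to brief, manageable grade 3 events.

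The cost is protocol wording; Table 6.3.2 does not change. The downside is that more events can end the doubling, so escalation may go through 600 mg/m² more often and be slower. The exclusion route in item 3 limits that.
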